8. PROTOCOL APPROVAL, STUDY MONITORING AND COMPLIANCE

Institutional Review Board

The clinical investigation, including the consent form, will be reviewed by an Institutional Review Board in accordance with Title 21 of the Code of Federal Regulations, Parts 50 and 56. Approval by the Board must be obtained prior to the initiation of the study.

The study will be conducted in compliance with Good Clinical Practice Regulations, the study protocol and protocol amendment(s). Designated personnel will audit this study to ensure protocol compliance. In addition, study data and the Final Report will be examined for completeness, accuracy and proper documentation.

Informed Consent and Other Written Information for Subjects

The informed consent form and any other written information for subjects should meet local requirements of language and interpretation. One copy of the signed informed consent form and any other written information will be given to the subject or legal representative and the original will be retained by the investigator in the study files. The informed consent form and any other written information prepared by the investigator must be reviewed and approved by the sponsor and by the Institutional Review Board prior to their implementation. The informed consent form must include all required elements in accordance with GCP guidelines.

Protocol Compliance

The investigator is obligated to follow the provisions and requirements of the study protocol accordingly. Any changes to the protocol must be implemented only through formal written protocol amendments and only upon joint approval by the sponsor and investigator. All protocol amendments must be reviewed and approved prior to implementation by the institutional review board. If a protocol amendment requires changes to the informed consent form, the revised consent form must also be approved by the sponsor and the IRB.

Departures from eligibility requirements may be allowed on a case-by-case basis by the medical monitor or other authorized sponsor representative. Such departures must be medically and scientifically justified, must be pre-authorized, and must be documented in the case report form and tracked as official eligibility waivers.

Study Monitoring

The study will be monitored by members of the Oral Care Clinical Research Department of Colgate-Palmolive at periodic intervals during the course of the study to ensure that the study is being conducted according to Good Clinical Practice Guidelines.

General Procedures

The Sponsor's study monitor will review the progress of the study as frequently as is necessary to ensure adequate and accurate data collection. Monitoring activities may include:

- Periodic on-site visits
- Telephone or virtual communications with the site
- Ongoing review of case report forms, clinical records, and administrative documents

All records pertaining to the study will be made available to the study monitor during each site visit. Routine monitoring visits will be planned and confirmed in advance, as much as possible, to allow adequate time to assemble these records. Unplanned visits may occur as dictated by study necessities.

Important agreements and discussions between the Sponsor and investigator should be documented for the study file. Examples include eligibility criteria exceptions, agreements to deviate from protocol-defined procedures, notifications of subject withdrawal, etc.

Reports

The final report for the sponsor will summarize the method, statistical analyses, data and conclusion relative to the test product, the subject completing the study and summarize any adverse events and deviations. Source data will be retained by the study site. Copies of the transcribed data will be incorporated in the final report as data tables.

Record Retention and Access to Source Data/Documents

Source documents must be kept for at least five (5) years after terminating the study. The Investigator will maintain all study documentation for all subjects entered into the study in a secure area, ensuring the confidentiality of the information collected. Securing records includes placing written forms in locked file cabinets and/or sealed and labeled storage boxes in a locked room. Access will be denied to all persons with the exception of the Principal Investigator and his/her designees. In the event that clinical records cannot be securely kept by the clinical site for the agreed upon duration of time, the study sponsor will be notified before the destruction of any study records occurs. The study sponsor maintains the right to keep the clinical records for the agreed duration of time.

9. STUDY PRODUCT MANAGEMENT

Study Products

Study products will be supplied by the sponsor for this study. The study investigator will verify that the quantity of supplies, protocol number, and identification numbers match the information on the shipping invoice, and will store and account for the study supplies as described below.

Study Products Storage, Handling, and Accountability

The study products must be stored in a secure area with limited access, at room temperature. The investigator is directly responsible for the accountability of all used and unused study products. The investigator and all sub-investigators will make every effort to remain blinded as to the subject regimen. Records must be maintained to document the receipt and disposition of all study supplies provided to the investigator by the sponsor. The study monitor will review these records periodically during the course of the study. At the end of the study, or as directed by the monitor, the investigator must return all unused study products to the sponsor.

10. CONCOMITANT THERAPY

If a subject takes concomitant medications as a matter of necessity for the treatment of a medical condition, then such medication may be permitted for the duration of the study at the discretion of the investigator. However, it is the responsibility of the investigator to disqualify from entering the study any subject who, upon screening, is using medication or consumer products that might obscure the interpretation of study results. All medications currently used by the subject at enrollment, or any time through the end of the study, will be recorded on medical history and visit form. Subjects may receive medication to treat adverse events as deemed necessary by the investigator or the subject's physician.

11. ADVERSE EVENTS

A. DEFINITIONS:

Adverse Events (AEs) and Serious Adverse Events (SAEs) are defined by the ICH Guideline for Good Clinical Practice (ICH GCP) as follows:

Adverse Event: Any untoward medical occurrence in a patient or clinical investigations subject administered a pharmaceutical product and which does not necessarily have to have a causal relationship with this treatment. An adverse event (AE) can therefore be any unfavorable and unintended sign (including abnormal laboratory finding), symptom, or disease temporally associated with the use of a medicinal product, whether or not considered related to the medicinal product.

AEs include any clinically significant deterioration of a subject's medical status, after being enrolled in the study and signing an Informed Consent form. The AE may involve any organs or systems and can be represented by the new onset or the deterioration of a disease, a syndrome, a symptom, a physical sign, as well as by findings and results of instrumental examinations and laboratory tests. Any medically relevant and untoward change from baseline, including frequency or pattern changes for a fluctuating condition (e.g., migraine), occurring after the first administration of study medication is an adverse event. All such occurrences must be recorded and reported accordingly, whether they appear causally related to the study medication, or not.

Serious Adverse Event: Any adverse event occurring at any dose that results in any of the following outcomes:

- Death
- Life threatening adverse event
- Inpatient hospitalization, or prolongation of existing hospitalization
- Persistent or significant disability/incapacity
- Congenital anomaly/birth defect

Important medical events that may not result in death, be life-threatening, or require hospitalization may be considered a serious adverse experience when, based upon appropriate medical judgment, they may jeopardize the patient or subject and may require medical or surgical intervention to prevent one of the outcomes listed in this definition.

Examples of such important medical events include allergic bronchospasm requiring intensive treatment in an emergency room or at home, blood dyscrasias or convulsions that do not result in inpatient hospitalization, or the development of drug dependency or drug abuse.

B. IMPORTANT NOTES:

The concepts of Adverse Event / Experience (AE) and Serious Adverse Event / Experience (SAE) represent regulatory instruments used to evaluate and monitor the safety of clinical trial subjects. Therefore, these terms only apply in light of their regulatory definition. The term "serious", in a regulatory sense, does not necessarily mean "severe". All adverse events (serious and non-serious) reported during a study will be taken into account when analyzing the study data and establishing the safety profile of the investigational drug, and will be included in the final study report. The SAE concept is primarily used to identify, during the conduct of the trial, those adverse events that may require an expedited reporting procedure to regulatory authorities.

Death: The outcome of death requires that the AE that resulted in death be reported as an SAE. Death, in and of itself, is not an AE; it is only an outcome. The cause of death is the AE; therefore, the investigator should make every effort to obtain and document the cause of death for all subjects who die during the study. If, despite all efforts, the cause of death remains unknown, the AE it should be documented as "unspecified fatal event".

Life-threatening Adverse Event: Any adverse event that places the patient or subject, in the view of the investigator, at immediate risk of death from the reaction as it occurred (i.e., it does not include a reaction that, had it occurred in a more severe form, might have caused death).

Hospitalization: It should be noted that hospitalization, in and of itself, does not represent an SAE. It is the adverse event leading to the subject's hospitalization that becomes "serious" when it requires

inpatient care. Consequently, SAE should not be reported in case of pre-planned hospitalizations for pre-existing conditions that did not worsen during the study.

Disability: A substantial disruption of a person's ability to conduct normal life functions.

C. REPORT AND DOCUMENTATION OF ADVERSE EVENTS:

Expected Adverse Effects:

To blood draws

- Hematoma and/or soreness at the site of the puncture

To Periodontal Treatment:

- Tooth sensitivity
- Oral bleeding
- Gingival swelling
- Possibly minor bruising, bleeding or soreness at the anesthesia injection site during application

To X-Ray (Full Mouth) Series -S0 and T5:

- This research study involves exposure to radiation from two full mouth series (14 periapicals and 4 vertical bitewing projections per series). Please note that this radiation exposure is not necessary for medical care and is for research purposes only.
- For comparison, the average person in the United States receives a radiation exposure of 0.3 rem (or 300 mrem) per year from natural background sources, such as from the sun, outer space, and from radioactive materials that are found naturally in the earth's air and soil.
- The dose that a subject will receive from participation in this research study is less than the amount received from these natural sources in one year.
- The amount of radiation the subjects will receive in this study has a minimal risk and is below the dose guideline established by The University of North Carolina Radiation Safety Committee for research subjects.

General Procedures for All Unexpected Adverse Events

All clinical complaints, symptoms, or signs that meet the adverse event definition, except expected adverse events listed above, will be recorded on the Non Serious Adverse Events case report form (CRF) using a recognized medical term or diagnosis that accurately reflects the event. Source documentation should be maintained that allows for clear identification of each adverse event and the following

parameters required for the CRF:

- AE description
- Date of onset
- Date of resolution
- Outcome

- Severity
- Seriousness
- Relationship to study drug (causality)
- Actions taken

Adverse events will be assessed by the investigator or designee for severity, relationship to the study product, possible etiologies, and whether the event meets the criteria as a serious adverse event and therefore requires immediate notification of the sponsor.

For CRF data collection purposes, the outcome of all adverse events recorded on the Adverse Event form should be reported within two (2) weeks of the study completion. The investigator will include this information in the Site Report providing a line listing using the Periodic/End of Study Report Form and attaching the individual adverse event form for each case reported. However, the investigator is responsible for following all adverse events until resolution or until no longer of clinical concern, and providing these data to the sponsor.

When protocol duration is six (6) months or longer, a Periodic/End of Study Report Form must be completed and included as part of your Site Report every six (6) months for the duration of the protocol.

Reporting Procedures for Serious Adverse Events

Any adverse event that is serious or potentially serious requires additional detailed reports and follow-up. A serious adverse event must be reported to the sponsor's representative immediately (within 24 hours of the investigator learning about the event). A Serious Adverse Event Report Forms must be completed so as to facilitate discussion and implementation of necessary follow-up measures, and to enable the sponsor to submit necessary reports to regulatory authorities and other investigators. Once the sponsor reviews the Serious Adverse Event Report Form, additional information may be requested from the investigator to allow appropriate medical evaluation and determine the regulatory reporting requirements.

The investigator is responsible for following all unexpected adverse events, especially those deemed "serious," until resolution or until the event is no longer of clinical concern, and for providing all data to the sponsor in an agreed-upon format. The investigator is also responsible for reporting all serious adverse events to the Institutional Review Board (IRB) overseeing the conduct of the study at the respective study center, according to the rules and procedures established by this committee.

12. SUBJECT TERMINATION/WITHDRAW PROCEDURES

A genuine effort will be made to determine the reason(s) why a subject fails to return for the necessary visit(s) or is dropped from the study. Subjects could be dropped from the study if any of the following occur:

1. Subject fails to substantially comply with the protocol requirements.
2. Subject fails to report for a scheduled examination.
3. Subject is treated with medication(s) during the course of the study, which may interfere with the parameters under study.
4. Subject receives emergency dental or medical treatment, which may interfere with the parameters under study.
5. Subject develops a serious adverse reaction. The Study Investigator will immediately notify the study monitor and information will be recorded on an Adverse Reaction Form.
6. Sponsor elects to terminate the study.
7. Subject elects to terminate participation in the study.

A study Visit Form indicating end of study participation must be completed for all subjects entered into the study even if they do not complete the study.

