14.1.2. Primary Analyses

Analyses associated with the first primary outcome, the impact of treatment on oral health measures, will be performed using generalized estimating equations (GEE) methods. Longitudinal outcomes in the Treated vs. Control groups will be compared and will include all subjects who were randomized and their data from visits T1 - T4 based on intent-to-treat (ITT) group assignment.

The second primary outcome, association between changes in oral health and changes in systemic health, will be evaluated using correlation analysis. Changes in the measures of oral and systemic health between Baseline (T0) and follow-up visit 4 (T4) will be calculated for all subjects in the study who complete the T4 visit. The strength of correlations between changes in oral health and change in HbA_{1c} (in subjects with prediabetes or type 2 diabetes) or change in flow mediated dilation will be evaluated.

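### Section 12 lets a randomised subject be dropped for non-compliance, a missed examination, or possibly interfering medication or emergency treatment, and nothing supplied says outcome assessments then continue for the ITT analysis

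*Combined protocol and SAP*

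**What the plan says.** **Grounds for a drop.** Section 12 opens its list with "Subjects could be dropped from the study if any of the following occur". Item 1 is "Subject fails to substantially comply with the protocol requirements". Item 2 is "Subject fails to report for a scheduled examination"; as worded, a single missed examination could suffice. Item 3 covers medication taken during the study that might interfere with the study parameters. Item 4 is "Subject receives emergency dental or medical treatment, which may interfere with the parameters under study". Items 5 to 7 (serious adverse reaction, sponsor termination, the subject's own withdrawal) are not at issue here.

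**What follows a drop.** Section 12 asks for an effort to learn the reason and for a form: "A study Visit Form indicating end of study participation must be completed for all subjects entered into the study". Section 11 keeps adverse-event follow-up going: "the investigator is responsible for following all adverse events until resolution or until no longer of clinical concern", and again "The investigator is responsible for following all unexpected adverse events". No comparable sentence covers periodontal, blood, vascular or questionnaire outcomes.

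**What the analysis needs.** Section 14.1.2 says that the first primary comparison "will include all subjects who were randomized and their data from visits T1 - T4 based on intent-to-treat (ITT) group assignment", fitted by GEE. Section 14.1.3 applies ITT and GEE to all secondary outcomes. The second primary analysis, the correlation of changes from T0 to T4, uses only subjects who complete T4.

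**The concern.** Items 1 to 4 are events after randomisation, and the rule removes the subject from the study rather than from the regimen alone. Followed literally, it can end collection of the later T1 to T4 outcomes on which the ITT comparison relies.

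The reasons may be related to arm or outcome. Repeat periodontal treatment at T1 to T3, home products, behavioural support and brushing-data review belong to the Treatment Group during that period (Sections 1.3 and 3.2), so that arm has more regimen to fail. Emergency dental treatment is plausibly related to periodontal status. The version history records that blinding language was removed from Section 4.1, so a discretionary drop may be made knowing the arm.

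Losing Treatment subjects who did not follow the regimen would tend to overstate the effect. Losing Control subjects who did badly would tend to understate it.

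**Working it through.** **1. The plan's own figure.** Inputs from Section 14.2: mean reductions 0.88 mm (SD 0.5) and 0.63 mm (SD 0.59), two-sided alpha 0.05, power 90%.
- Difference: 0.88 - 0.63 = 0.25 mm. Common SD: sqrt((0.5² + 0.59²)/2) = 0.547.
- n per group = 2 × (1.960 + 1.282)² × 0.547² / 0.25² = 100.6, so 101 against the stated 100. Power at 100 per group is 89.8%.
- Dropout: 100/0.9 = 111.1, so 112 per group and 224 in total, as stated.

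The sample size reproduces. The point is not an arithmetic error.

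**2. Assumptions for the illustration.** The documents give neither a rate for drops under items 1 to 4 nor a working correlation. I therefore assume that 10% of one arm is affected and that all of them are dropped, take the 0.25 mm effect as constant over T1 to T4 (Section 14.2 states it only as a 12-month difference), and show working independence and an exchangeable correlation of 0.5.

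**3. Method.** Let k = 0, 1, 2, 3 be the visits recorded before the drop. A subject with n visits carries weight w_n = n/(1 + (n-1)ρ), with w_0 = 0. For ρ = 0.5, w_1 to w_4 are 1, 1.333, 1.5 and 1.6. Each arm mean is the weighted mean of its retained and dropped subjects.

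**4. Case A: Treatment non-compliers with the Control mean.** The full ITT difference is 0.9 × 0.25 = 0.225 mm. Relative bias = w_4/(0.9 w_4 + 0.1 w_k) - 1. At k = 0 this is 1/0.9 - 1 = 11.1% (0.250 mm reported).

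**5. Case B: Control subjects who do worse.** The overall Control mean stays at 0.63, so the full difference is 0.25 mm.
- Half an SD worse: dropped mean 0.63 - 0.295 = 0.335; retained mean (0.63 - 0.0335)/0.9 = 0.6628. At k = 0 the difference is 0.88 - 0.6628 = 0.217 mm, or -13.1%.
- One SD worse, an extreme with almost no response: dropped mean 0.04; retained mean (0.63 - 0.004)/0.9 = 0.6956. At k = 0 the difference is 0.184 mm, or -26.2%.

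**6. Case A and half-SD case B together, 10% in each arm.** The full difference is 0.855 - 0.63 = 0.225 mm. At k = 0 the reported difference is 0.88 - 0.6628 = 0.217 mm, or -3.5%.

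| Relative bias | Before T1 | After T1 | After T2 | After T3 |
|---|---|---|---|---|
| A, ρ = 0 | +11.1% | +8.1% | +5.3% | +2.6% |
| A, ρ = 0.5 | +11.1% | +3.9% | +1.7% | +0.6% |
| B half SD, ρ = 0 | -13.1% | -9.6% | -6.2% | -3.0% |
| B half SD, ρ = 0.5 | -13.1% | -4.6% | -2.0% | -0.7% |
| B one SD, ρ = 0 | -26.2% | -19.1% | -12.4% | -6.1% |
| B one SD, ρ = 0.5 | -26.2% | -9.2% | -4.0% | -1.5% |
| A and B half SD, ρ = 0 | -3.5% | -2.5% | -1.6% | -0.8% |
| A and B half SD, ρ = 0.5 | -3.5% | -1.2% | -0.5% | -0.2% |

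Adding visit terms to the GEE moves these figures by at most 0.4 percentage point. If only half of the affected subjects are dropped, case A falls to between 5.3% and 0.3%.

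**The case against.** **The rule is permissive and other sections soften it.** Section 12 says that subjects may be dropped, not that they must be. Sections 1.3 and 5.2 provide support for poor adherence, Section 3.1 allows 28 days either side of each visit, Section 10 permits necessary medication, and Section 2.2 provides site-directed care in the Control Group. All of this should make drops less common. None of it says that assessments continue after one. Section 8 mentions agreed deviations and withdrawals as things to document, but is equally silent on assessments.

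**GEE keeps earlier visits.** This stands and is built into the calculation. It is why late drops matter little. Under item 2 the missed examination is lost in any case; only the visits after it are at stake.

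**The largest figures are strained.** This also stands. Brushing data and clinical progress are next reviewed at T1, so a drop before T1 for those reasons is unlikely, though one under items 3 or 4 is possible. One-arm cases also leave out offsetting losses in the other arm. The offset is itself an assumption, however: with the one-SD Control case at 10% in each arm, the net before T1 is still 0.1844/0.225 - 1 = -18%.

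**Stronger readings that the text does not support.**
- A reader might infer that dropped subjects leave the ITT set. No section removes them.
- A reader might infer a loss of power. Section 14.2 allows further recruitment, which can restore numbers, though not the missing outcomes.
- A reader might see a contradiction between item 3 and Section 10. Both are discretionary and can be read together, so only a clarification is needed.
- A reader might conclude that missing data are not handled at all. Sections 2.6 and 14.1.4 point to a Statistical Analysis Plan whose separate text was not supplied, so this cannot be judged.

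**Conclusion.** The point holds as a gap between the withdrawal rule and the ITT analysis. Section 12 can end outcome collection for reasons that may be informative, and no supplied section says otherwise. The comparison could be biased, in a direction that the documents do not settle.

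Under the stated assumptions, the illustrative size is +11% to +0.6% for Treatment non-compliers. For Control subjects it is -13% to -0.7% at half an SD worse, and -26% to -1.5% at an extreme one SD. With case A and the half-SD case B in both arms it is about -3.5% to -0.2%. These are not predictions: the drop rate, who is dropped, the correlation and the constant effect are all assumed. Only drops before T1 reach the large ends. The change is worth making because it costs little and no analysis can recover outcomes that were not collected.

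**What to change.** **Section 12.** Separate deviation from the study regimen from the end of data collection. Record items 1 to 4 as dated events. Continue the endpoint assessments already scheduled (periodontal examination, bloods including HbA1c, FMD and IMT, PANAS and PMT) through T4 and the FMD/IMT session about 8 weeks after it. Stop them only if consent is withdrawn, the subject is lost, the study ends, or the investigator judges the assessments unsafe. Clinical management, including any treatment at T4, stays with the existing protocol and the investigator.

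**Section 14.1.2.** State that data collected after such events remain in the ITT analysis, and report events and losses by arm, visit and reason.

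**Clarification.** Say how item 3 is to be read alongside Section 10.

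**Conditional.** If the separate Statistical Analysis Plan has no missing-data sensitivity analysis, add one, for example delta-adjusted by arm over a stated range.

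**Cost.** A formal amendment with joint approval and IRB review under Section 8, and a revised consent form if affected; a modest retention effort; and at most one extra analysis. No new visits or samples are needed.
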